## 4.5. Screening/ Run-in Failures

If a blood sample has been collected and it is determined that the subject does not meet the inclusion and exclusion criteria for participation in the study, then the investigator must complete the appropriate documentation to request sample destruction within the timeframe specified by GSK.

# 5. STUDY TREATMENTS

## 5.1. Investigational Product and Other Study Treatment

Tenofovir disoproxil fumarate (9-[(R)-2-[[bis[[(isopropoxy-carbonyl) oxy] methoxy] phosphinyl] methoxy] propyl] adenine fumarate (1:1)); GS4331-05) is an oral pro-drug

(bisPOC-PMPA) of TFV (PMPA), an acyclic nucleoside phosphonate (nucleotide) analogue of adenosine 5'-monophosphate. TDF has demonstrated antiviral activity against HBV and HIV and is indicated for use in combination with other antiretroviral agents in the treatment of HIV infection.

Tenofovir disoproxil fumarate tablets are white, almond-shaped, film-coated tablets containing 300 mg of TDF, debossed with "GILEAD" and "4331" on one side of the tablet. Each tablet contains the following inactive ingredients: microcrystalline cellulose, lactose monohydrate, pregelatinised starch, croscarmellose sodium, and magnesium stearate. The tablets are film coated with Opadry II White 32K18425.

TDF are packaged in white, high-density polyethylene bottles with a white child resistant cap. There are 30 tablets per bottle. Each bottle also contains silica gel canister(s) to protect the product from humidity and fibre packing to protect the product during handling and shipping.

For subjects who do not achieve satisfied response to TDF will add another drug without cross resistant to TDF including LAM (Heptodin, GlaxoSmithKline, 100mg QD), ETV (Baraclude, Bristol-Myers Squibb,0.5mg QD) and LdT(Sebivo,Novartis,600mg QD). Investigator will make the decision for the drug selection.

The contents of the label will be in accordance with all applicable regulatory requirements.

### 5.1.1. Handling and Storage of Investigational Product

No preparation of investigational product is required at site.

Under normal conditions of handling and administration, investigational product (IP) is not expected to pose significant safety risks to site staff. A Material Safety Data Sheet describing the occupational hazards and recommended handling precautions will be provided to site staff if required by local laws or will otherwise be available from GlaxoSmithKline upon request.

Investigational product must be stored in a secure area under the appropriate physical conditions for the product at room temperature lower than 30° C. Access to and administration of the IP will be limited to the Investigator and authorised site staff. Investigational product must be dispensed or administered only to subjects enrolled in the study and in accordance with the protocol.

### 5.1.2. Dosage and Administration

Subjects will be assigned to receive Tenofovir disoproxil fumarate (TDF) 300 mg once daily during the study period.

Subjects will be instructed to return unused study medication in the original container at each post-baseline study visit. The Investigator will be responsible for maintaining accurate records for all study drug and study drug bottles dispensed and returned. The inventory must be available for inspection by the study monitor. Study medication

supplies, including partially used or empty bottles, must be accounted for and the dispensing logs must be verified by the study monitor prior to destruction or return.

#### Dose reduction in the patients with renal insufficiency

If subjects develop renal insufficiency (defined by serum creatinine clearance) during study treatment, the following dose reduction criteria should be used when subjects have a serum creatinine clearance of <50 ml/minute:

Calculated	Requiring Haemodialysis			
≥ 50	30-49	10–29		
TDF 300 mg every 24 h	TDF 300 mg every 48 h	TDF 300 mg every 72 h	TDF 300 mg every 7 days or after a total of approximately 12 h of dialysis b	
LAM tablets 100mg every 24h	Use	of LAM tablets is prohil	bited	
ETV tablets 0.5mg every 24h	ETV tablets 0.5mg every 48h	ETV tablets 0.5mg every 72h	ETV tablets 0.5mg every 5 to 7 days c	
LdT tablets 600mg every 24h	LdT tablets 600mg every 48h	LdT tablets 600mg every 72h	LdT tablets 600mg every 96h d	

a. Calculated using ideal (lean) body weight.

b. Generally once weekly assuming three haemodialysis sessions a week of approximately 4 h duration. Medication should be administered following completion of dialysis.

c. If administered on a hemodialysis day, administer ETV after the hemodialysis session.

d. When administered on hemodialysis days, administer LdT after hemodialysis.

## 5.2. Treatment Assignment

This is an open label, single arm study.

## 5.3. Blinding

NA

## 5.4. Product Accountability

In accordance with local regulatory requirements, the investigator, designated site staff, or head of the medical institution (where applicable) must document the amount of investigational product dispensed and/or administered to study subjects, the amount returned by study subjects, and the amount received from and returned to GSK, when applicable. Product accountability records must be maintained throughout the course of the study.

## 5.5. Treatment Compliance

The importance of compliance with the treatment regimen will be emphasised at each visit.

The subject must be reminded to return all unused medication (including empty containers). The Investigator or designated study site personnel should count the number of tablets returned by the subject to establish the number of tablets used, and compare this to the number of tablets expected to be used for the period. A record of this reconciliation must be maintained using the accountability forms provided, and any issues of non-compliance discussed with the subject.

## 5.6. Concomitant Medications and Non-Drug Therapies

### 5.6.1. Permitted Medications and Non-Drug Therapies

All concomitant medication and the reason(s) for their use must be entered into the eCRF. Effort should be made to give only medications which are clearly indicated for a specific medical reason.

## 5.6.2. Prohibited Medications and Non-Drug Therapies

No other investigational drugs, immunosuppressive therapies, immunomodulatory therapies (including IFN or thymosin  $\alpha$ ), systemic cytotoxic agents, oral antiviral agents (e.g., didanosine, LAM, ADV, ETV, LdT, other medicinal products containing TDF, ganciclovir, famciclovir, FTC, DAPD, LFMAU, HBIg), agents containing glycyrrhizic acid(e.g., compound glycyrrhizin, compound ammonium glycyrhetate, diammonium glycyrrhizinate), agents containing bicyclol or bifendate will be permitted except for the drugs which are allowed in the protocol.

TDF should be avoided with concurrent or recent use of a nephrotoxic agent including but are not limited to cidofovir, acyclovir, valacyclovir, ganciclovir, valganciclovir, aminoglycosides (e.g., gentamicin), high-dose or multiple NSAIDs,,and herbal medications (e.g., tripterygium wilfordii, leonuri and plant medicine containing aristolochic acid).

Traditional Chinese medicines and other herbal medicines intended to improve/protect liver function are prohibited during the study and must be discontinued at the time of screening. Such medicines include, but are not restricted to, oxymatrine and agents containing schisandra.

In the events mentioned in Section 6.3.1, medicines intended to improve/protect liver function will be allowed based on the Investigator's judgement after consulting with the GlaxoSmithKline medical monitor. All concomitant medication and reasons for their use must be entered into the eCRF. However, agents containing bicyclol, bifendate or schisandra will not be permitted in any situation.

## 5.7. Treatment after the End of the Study

No post-study medication is provided as part of this protocol.

Discontinuation of anti-HBV therapy, including VIREAD, may be associated with severe acute exacerbations of hepatitis and must only take place under careful supervision.

The investigator is responsible for ensuring that consideration has been given to the poststudy care of the patient's medical condition whether or not GSK is providing specific post study treatment. TDF study medication is commercially available in China.

## 5.8. Treatment of Study Drug Overdose

If a subject in the study takes an overdose, whether intentional or otherwise, the subject will be referred to a hospital at the Investigator's discretion. In these circumstances it is the responsibility of the Investigator to obtain as much clinical data as possible, including blood samples to determine TDF, LAM, LdT or ETVdrug levels, and to communicate this to GlaxoSmithKline. An SAE form must be completed if the overdose is associated with any signs or symptoms. For the purposes of this study, an overdose will be defined as any dose administration exceeded the recommended dose of TDF 300 mg, LAM 100mg, LdT 600mg or ETV 0.5mg per day.

201215

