## 1.3. Benefit:Risk Assessment

Summaries of findings from both clinical and non-clinical studies conducted with TDF can be found in the Investigator's Brochure and China-specific prescribing information for TDF in CHB. The following section outlines the risk assessment and mitigation strategy for this protocol:

Potential Risk of Clinical Significance	Data/Rationale for Risk	Mitigation Strategy								
Investigational Product (IP)										
Renal toxicity	TDF is principally eliminated by the kidney. Renal impairment, including cases of acute renal failure and Fanconi syndrome (renal tubular injury with severe hypophosphatemia), has been reported with the use of VIREAD	
 
Exclusion of CHB patients with creatinine clearance <70 ml/min
 
Monitor renal function every 12 weeks
 
Dosing interval adjustment of VIREAD is recommended in all patients with creatinine clearance below 50 ml/min.
 
All study drugs should be permanently discontinued in the event that repeat testing
 
								

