#### 6.3.2.1. Definition of an AE

Any untoward medical occurrence in a patient or clinical investigation subject, temporally associated with the use of a medicinal product, whether or not considered related to the medicinal product.

Note: An AE can therefore be any unfavorable and unintended sign (including an abnormal laboratory finding), symptom, or disease (new or exacerbated) temporally associated with the use of a medicinal product. For marketed medicinal products, this also includes failure to produce expected benefits (i.e., lack of efficacy), abuse or misuse.

Events meeting the definition of an AE include:

- Exacerbation of a chronic or intermittent pre-existing condition including either an increase in frequency and/or intensity of the condition
- New conditions detected or diagnosed after study treatment administration even though it may have been present prior to the start of the study
- Signs, symptoms, or the clinical sequelae of a suspected interaction
- Signs, symptoms, or the clinical sequelae of a suspected overdose of either study treatment or a concomitant medication (overdose per se will not be reported as an AE/SAE) unless this is an intentional overdose taken with possible suicidal/self-harming intent. This should be reported regardless of sequelae.

"Lack of efficacy" or "failure of expected pharmacological action" per se will not be reported as an AE or SAE. However, the signs and symptoms and/or clinical sequelae resulting from lack of efficacy will be reported if they fulfil the definition of an AE or SAE.

The signs and symptoms and/or clinical sequelae resulting from lack of efficacy will be reported if they fulfill the definition of an AE or SAE. Also, "lack of efficacy" or "failure of expected pharmacological action" also constitutes an AE or SAE.

Events that **do not** meet the definition of an AE include:

- Medical or surgical procedure (e.g., endoscopy, appendectomy); the condition that leads to the procedure is an AE
- Situations where an untoward medical occurrence did not occur (social and/or convenience admission to a hospital)
- Anticipated day-to-day fluctuations of pre-existing disease(s) or condition(s) present or detected at the start of the study that do not worsen
- The disease/disorder being studied, or expected progression, signs, or symptoms of the disease/disorder being studied, unless more severe than expected for the subject's condition

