#### 6.3.3. Laboratory and Other Safety Assessment Abnormalities Reported as AEs and SAEs

Any abnormal laboratory test results (hematology, clinical chemistry, or urinalysis) or other safety assessments (e.g., ECGs, radiological scans, vital signs measurements), including those that worsen from baseline, and felt to be clinically significant in the medical and scientific judgement of the investigator are to be recorded as AEs or SAEs. However, any clinically significant safety assessments that are associated with the underlying disease, unless judged by the investigator to be more severe than expected for the subject's condition, are not to be reported as AEs or SAEs.

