# 6.3.9. Prompt Reporting of Serious Adverse Events and Other Events to GlaxoSmithKline

Serious adverse events, pregnancies and liver function abnormalities meeting pre-defined criteria will be reported promptly by the Investigator to GlaxoSmithKline as described in the following table once the Investigator determines that the event meets the protocol definition for that event.

	Initial	Reports	Follow-up Information on a Previous Report			
Type of Event	Time Frame	Documents	Time Frame	Documents		
All SAEs	24 h	"SAE" data	24 h	Updated "SAE"		
		collection tool		data collection tool		
Pregnancy	2 Weeks	Pregnancy	2 Weeks	Pregnancy Follow-		
		Notification Form		up Form		
Adverse Drug	5 calendar	ADR	5 calendar days	ADR Follow-up		
Reaction	days	Form	-	Form		
(ADR)						

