## 6.3.10. Serum Creatinine Elevation

Serum creatinine values  $\ge 0.5 \text{ mg/dL}$  above baseline should be confirmed by repeat testing within 3 calendar days of receipt of results.

For serum creatinine elevations  $\geq 0.5 \text{ mg/dL}$  above baseline, subjects may continue all study medication, but it is recommended that subjects be monitored weekly until the serum creatinine returns to the original baseline value or  $\leq 0.3 \text{ mg/dL}$  from baseline.

All study drugs should be permanently discontinued in the event that repeat testing of serum creatinine confirms >2.0 mg/dL. The subject should be followed weekly until the serum creatinine reaches within 0.3 mg/dL of the baseline value.

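### The overdose definition in Protocol 5.8 uses the unadjusted daily doses, so a subject on a lengthened renal dosing interval can take 2 or 3 times the assigned amount without meeting it

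*Protocol*

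**What the plan says.** Protocol 5.8 gives one overdose definition for the whole study: "defined as any dose administration exceeded the recommended dose of TDF 300 mg, LAM 100mg, LdT 600mg or ETV 0.5mg per day". It mentions neither renal function nor section 5.1.2. When an overdose occurs, intentional or not, the investigator is to gather clinical data, including blood samples for drug levels, and inform the sponsor. If there are signs or symptoms, an SAE form is required.

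The renal table in Protocol 5.1.2 applies when clearance falls below 50 ml/min on study. For TDF, ETV and LdT it leaves the single dose unchanged and lengthens the interval. For TDF at 30-49 ml/min the entry is "TDF 300 mg every 48 h", and at 10-29 ml/min the interval is 72 h. ETV and LdT follow the same pattern. LAM is prohibited below 50 ml/min. The risk table in Protocol 1.3 lists the interval change among its measures against renal toxicity: "Dosing interval adjustment of VIREAD is recommended in all patients with creatinine clearance below 50 ml/min".

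Protocol 6.3.2.1 treats signs and symptoms of a suspected overdose as AEs, but states that "overdose per se will not be reported as an AE/SAE" unless it is an intentional overdose with possible self-harming intent.

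**The concern.** Where a dose reduction works only through the interval, a fixed daily ceiling cannot recognise an interval error. The likely error is simple: a subject is told to move to alternate days and keeps the daily habit. Section 5.8 covers unintentional overdose, so this falls within its purpose, yet its definition returns no.

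Two things are lost. If there are no symptoms, 6.3.2.1 does not make the excess itself reportable, so 5.8 is the section that would prompt drug levels and a message to the sponsor. If there are non-serious symptoms, the 5.8 SAE form (24 h under Protocol 6.3.9) is not prompted by the overdose rule. The event follows the ordinary AE route, or the ADR route with its "5 calendar days". The subjects concerned are those whose clearance of tenofovir is already reduced.

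**Working it through.** **Inputs**

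- Ceilings per day (Protocol 5.8): TDF 300 mg, LdT 600 mg, ETV 0.5 mg.
- Doses and intervals (Protocol 5.1.2): the same single doses every 24 h at 50 ml/min or above, every 48 h at 30-49 and every 72 h at 10-29.
- Visit spacing (Protocol Table 1): 12 weeks, or 84 days.
- Bottle size (Protocol 5.1): 30 TDF tablets.

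**Step 1: where the ceiling comes from.** For these three drugs the 5.8 figures equal the 5.1.2 doses for clearance of 50 ml/min or above. Within that band the definition works.

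**Step 2: assigned average per day against the ceiling.** Assigned average = dose x 24 / interval in hours. The ratio is for one full dose taken every 24 h.

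| Band | Drug | Assigned average per day | Taken per day | Ratio | Above 5.8 ceiling? |
|---|---|---|---|---|---|
| 30-49 | TDF | 300 x 24/48 = 150 mg | 300 mg | 2 | No, equal |
| 30-49 | ETV | 0.5 x 24/48 = 0.25 mg | 0.5 mg | 2 | No, equal |
| 30-49 | LdT | 600 x 24/48 = 300 mg | 600 mg | 2 | No, equal |
| 10-29 | TDF | 300 x 24/72 = 100 mg | 300 mg | 3 | No, equal |
| 10-29 | ETV | 0.5 x 24/72 = 0.167 mg | 0.5 mg | 3 | No, equal |
| 10-29 | LdT | 600 x 24/72 = 200 mg | 600 mg | 3 | No, equal |

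**Step 3: TDF over one visit period.** A 48 h schedule assigns 84/2 = 42 tablets, and daily intake uses 84, which is 84/42 = 200%. A 72 h schedule assigns 84/3 = 28, and daily intake is 84/28 = 300%. These totals assume a full daily supply in hand and the interval in force for all 84 days. The documents do not give the quantity dispensed after an interval change. If it were two bottles on a 48 h schedule, the total could not exceed 60/42 = 143%. One bottle on a 72 h schedule gives 30/28 = 107%. Supply caps the total, but daily intake runs at 2 or 3 times the assigned rate while tablets last.

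**Step 4: how far the 3x case can arise.** Protocol 6.3.10 states: "All study drugs should be permanently discontinued in the event that repeat testing of serum creatinine confirms >2.0 mg/dL". By the Appendix 1 formula, clearance at creatinine 2.0 mg/dL = (140 - age) x ideal weight x (0.85 if female) / (72 x 2.0). The assumed subjects are women of 158 cm (ideal weight 50.6 kg) and men of 170 cm (65.9 kg), aged 65 and 40, with actual weight not below ideal.

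- Woman of 65: 22.4 ml/min
- Woman of 40: 29.9 ml/min
- Man of 65: 34.3 ml/min
- Man of 40: 45.8 ml/min

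Of these four, only the older woman has real room in the 10-29 band before the stop. The 2x case at 30-49 is the main one.

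**The case against.** The strongest reply is that excess intake has other routes to notice.

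- Protocol 5.5 has the site count returned tablets, compare them with the number expected and discuss non-compliance. Table 1, note 15, requires reconciliation at each visit, and 5.1.2 has the study monitor verify the dispensing logs.
- SAP 7.1 makes more than 120% of the required tablets a deviation category that is both summarised and listed. SAP 7.3.3 lists expected and actual amounts and compliance by subject.
- Symptoms of a suspected overdose are AEs under 6.3.2.1. Under 6.3.3, laboratory changes "felt to be clinically significant in the medical and scientific judgement of the investigator are to be recorded as AEs or SAEs". SAP 7.5.3 counts clearance below 50 ml/min.
- A single ceiling is easy for sites to apply.

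All of this stands, and it limits the weight of the point. A reader might infer that the excess would go unseen; the documents do not support that. But none of these routes makes the case an overdose under 5.8 or prompts its drug-level samples and notification. The SAP percentage also shows the excess only if the expected amount follows the lengthened interval. Against a daily expectation, 84/84 = 100% raises no flag.

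It can also be argued that the recommended dose in 5.8 means the renally adjusted one. The sentence closes that reading by giving the amounts per day, and they are the unadjusted amounts.

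Two other extensions do not hold:

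- A reader might count LAM taken below 50 ml/min as a further gap, since 100 mg a day does not exceed the 5.8 figure. That use is already prohibited by 5.1.2 and falls under the SAP 7.1 deviation category for prohibited medication. It is use of a prohibited drug, and it need not be called an overdose.
- A reader might infer that renal monitoring itself fails, because clearance can fall below 50 ml/min before creatinine rises by 0.5 mg/dL. The interval change depends on clearance, assessed every 12 weeks (Protocol 1.3.1), not on that rise. A subject on a longer interval has already been identified.

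**Conclusion.** The point holds, and it is minor. For a subject moved to a longer interval under 5.1.2, the 5.8 definition gives the wrong answer. Continued daily dosing of TDF, ETV or LdT is 2 times the assigned amount at 30-49 ml/min and 3 times at 10-29 ml/min, and it is never above the ceiling. These ratios follow directly from the two sections. The ages, heights and dispensed quantities in the working are assumptions that serve only to illustrate how far the problem can reach.

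The documents do not give the number of subjects affected, and none is estimated here. It is likely small, because entry excludes clearance below 70 ml/min (Protocol 4.3), study drugs stop at a confirmed creatinine above 2.0 mg/dL, and ETV and LdT are used only as rescue therapy. What is lost is a specific safety action. The primary endpoint is not affected.

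**What to change.** In Protocol 5.8, define overdose as intake above the dose and interval currently assigned to the subject under 5.1.2. Keep the present daily ceiling for clearance of 50 ml/min or above. For a subject on a lengthened interval, state one tolerance: overdose means full doses on two consecutive calendar days. Leave LAM below 50 ml/min to the existing prohibition and its deviation category.

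The SAP limit of 120% should not serve as the trigger. Over 84 days on a 48 h schedule it allows 42 x 1.2 = 50.4 tablets. Sixteen consecutive daily doses followed by alternate-day dosing for the other 68 days use 16 + 34 = 50 tablets. Sixteen days at twice the assigned rate would then pass, and a count may come up to 12 weeks late, when a drug level may no longer reflect the excess.

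The two-day rule has a limit of its own. Alternate-day dosing on a 72 h schedule (72/48 = 1.5 times the assigned amount) would not trigger it and would be left to the tablet count.

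The cost is one or two sentences, plus a few more overdose reports and drug-level samples from subjects with reduced clearance. No dose, endpoint or analysis changes.

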## 6. STUDY ASSESSMENTS AND PROCEDURES

#### Table 1Time and Events Table

Procedures	Screening 	Baseline (Day 0)		Treatment Period (Week) 								Additional Visit	Early Withdrawal			
	(≤4 weeks	(Duy 0)											Subjects who	(Week off treatment)		
	dosing)		12w± 6days	24w± 6days	36w± 6days	48w± 6days	60w± 6days	72w± 6days	84w± 6days	96w± 6days	108w± 6days	120w± 6days	132w± 6days	144w± 6days	do not achieve satisfied response to	12w±6days
	Visit	Visit	Visit	Visit	Visit	Visit	Visit	Visit	Visit	Visit	Visit	Visit	Visit	Visit	TDF	
	1	2	3	4	5	6	7	8	9	10	11	12	13	14		
Written informed consent																
Subject demography 	$\checkmark$															
Medical history	$\sqrt{4}$	$\sqrt{5}$														
Inclusion/exclusion criteria	$\checkmark$															
Concomitant medication 		$\checkmark$	$\checkmark$	$\checkmark$	$\checkmark$		$\checkmark$			$\checkmark$	$\checkmark$		$\checkmark$	$\checkmark$		$\checkmark$
Physical examination7	$\checkmark$	$\checkmark$	$\checkmark$	$\checkmark$	$\checkmark$		$\checkmark$			$\checkmark$	$\checkmark$		$\checkmark$	$\checkmark$		$\checkmark$
Vital signs 	$\checkmark$	$\checkmark$	$\checkmark$	$\checkmark$	$\checkmark$		$\checkmark$			$\checkmark$	$\checkmark$		$\checkmark$	$\checkmark$		$\checkmark$
Adverse events		$\checkmark$	$\checkmark$	$\checkmark$	$\checkmark$	$\checkmark$	$\checkmark$			$\checkmark$	$\checkmark$	$\checkmark$	$\checkmark$	$\checkmark$		$\checkmark$
Serious adverse events		$\checkmark$	$\checkmark$	$\checkmark$	$\checkmark$	$\checkmark$	$\checkmark$			$\checkmark$	$\checkmark$	$\checkmark$	$\checkmark$	$\checkmark$		$\checkmark$
Laboratory assessments																
Haematology	$\checkmark$	$\checkmark$		$\checkmark$												$\checkmark$

